## **6.2 Patient Follow-up Criteria – HCP Process**

Patients who discontinue full registry participation prior to completing the registry 10 years of follow-up will be offered to participate in the direct to HCP (Health Care Provider) follow-up process, as allowed by applicable local regulations. In order to participate in the direct to HCP follow-up process, the parent or guardian of the patient must sign and date the consent/patient authorization form. Pediatric patients will be included in all discussions as per applicable local regulations in order to obtain verbal or written assent. Patients participating in the HCP follow-up process may not switch registry treatment arms during the HCP follow-up process. To switch to the Humira arm (add on or switch to Humira), an MTX patient following the direct to HCP follow-up process must re-consent at a registry investigative site. The treatment arm at the time of patient authorization will be noted. All data collected post authorization will be included in analysis of the treatment arm indicated at the time of patient authorization, or until the date the patient re-consents in the registry.

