#### **6.5 Registry Duration**

The planned follow-up observation period is 10 years from enrollment into one of the treatment arms. The follow-up period for patients that switch from the MTX arm to the Humira arm will begin when they enroll into the Humira arm, in which case participation would be longer (i.e., up to 10 years from the time of the switch).

A patient may withdraw from the registry at any time without prejudice. If the physician decides it is in the best interest of the patient to discontinue Humira or MTX for any reason, treatment should be stopped. Physicians are encouraged to keep patients in the registry for a full 10-year observation period irrespective of future treatment decisions so important and complete safety and effectiveness information can be obtained. If the patient is not seen at a visit, efforts, i.e., phone, fax, letter, will be made to gather safety data through Year 10.

Patients in the MTX arm who are prescribed Humira treatment must be re-consented before enrolling in the Humira arm during the time that the enrollment period is open (i.e., until enrollment in the Humira treatment arm is complete).

If a patient withdraws or is withdrawn from the registry, this should be noted, along with the reason for withdrawal on the electronic study completion page. At the time of withdrawal from the registry, an assessment of the patient's current medical condition will be completed.

Patients who discontinue from the registry or transition to another HCP will be offered to participate in the direct to HCP follow-up process by their registry physician, as allowed

by applicable local regulations. If the patient (or Parent/Guardian for pediatric patients) agrees, a consent/assent and/or patient authorization for use/disclosure for data (as applicable) will be obtained.

Effectiveness measures will not be collected from patients participating in the direct to HCP process.

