#### **6.6.4 Prior and Concomitant Medications**

Any DMARD and biologic treatments previously administered and the reason for discontinuation (i.e., AE, lack of effectiveness, intolerance or other) will be recorded. Information on the highest maintained dose, date of last administration, length of time on the medication and reason for stopping the medication will be collected in the source documents and appropriate eCRF pages.

Any medication or vaccine (including over-the-counter or prescription medicines, vitamins and/or herbal supplements) that the patient is receiving at the time of screening, and/or receives during the registry, must be recorded along with the reason for use, date(s) of administration including start and end dates, and dosage information including dose, route and frequency on the appropriate eCRF.

Intra-articular and/or soft-tissue corticosteroid injections must be captured, however the joint that is injected should be considered non-evaluable for 3 months thereafter.

Kineret® (anakinra), Orencia® (abatacept), Rituxan® (rituximab), Enbrel® (etanercept), Remicade® (infliximab) or other approved biologic agents are not to be given concurrently while participating in the registry as per the labeling for MTX and Humira.

Patients should not be enrolled into the MTX arm if they have had prior treatment with any investigational agents or anti-rheumatic biologic therapies such as, but not limited to, Orencia® (abatacept), Enbrel® (etanercept), Remicade® (infliximab), Rituxan® (rituximab), or Actemra® (tocilizumab). Patients in the MTX arm may be prescribed and treated with MTX alone, or in combination with other DMARDs but not with anti-TNFs or other biologic therapies at the time of enrollment.

Patients in MTX arm that require treatment with the biologic/anti-TNF will be excluded from the MTX treatment arm but may continue within the registry. After the Humira treatment arm enrollment is complete, if a patient in MTX treatment arm begins Humira therapy, Humira will be considered a concomitant medication.

Except for live vaccines, patients may still receive vaccines while on Humira. It is recommended that children with JIA be brought up to date with all immunizations prior to starting Humira.

The AbbVie Study Designated Physician identified in Section 7.1.8 should be contacted if there are any questions regarding concomitant or prior therapies.

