### **7.3 Data Collection Procedures for Patients Who Participate in the Direct to HCP Process**

For patients participating in the direct to HCP process, HCPs will document any Adverse Event of Special Interest, hospitalizations, surgeries, and death as defined in Section 7.1.3 annually via a paper questionnaire or eCRF through the first 5 years of the patient's enrollment date in the registry. HCPs will document any occurrence of hospitalizations, surgeries, death, malignancies, and CHF annually via a questionnaire or eCRF beginning at Year 6 through Year 10. HCPs will document any occurrence of a subset of AESI that includes congestive heart failure and malignancies, hospitalizations, surgeries, and death

annually via a questionnaire or eCRF beginning at Year 6 through Year 10. For polyarticular JIA patients 2 to < 4 years of age in countries with available local approval for this group of patients at the time of consent to the registry the AESI, hospitalizations, surgeries and death will be collected for the full 10 years as defined by the protocol (Figure 2). The HCP will collect and record the date of onset (where known), and description of the event. The use of other medications used to treat polyarticular JIA, and the start and stop dates for Humira and/or MTX will be collected on an annual basis.

Effectiveness data will not be collected as part of the direct to HCP process.

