### **10.3.1 Analysis of Observational SAEs and AEs of Special Interest**

The number and percent of patients experiencing SAEs and AEs of Special Interest during the registry, regardless of whether the AEs are reported during or after the Humira or MTX treatment, will be tabulated by body system and Medical Dictionary for Drug Regulatory Activities (MedDRA®) preferred term. Rates (event per 100 patient year of observation) of SAEs and AEs of Special Interest and the 95% confidence interval will be provided. The AEs summaries will also include SAEs and AEs of Special Interest collected through the HCP process. The last contact date is defined as the last date of registry or direct to HCP process participation, whichever occurs later.

The summaries will be provided using data from the first day in registry through the last contact irrespective of drug treatment duration.

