## **10.6 Determination of Sample Size**

The proposed sample size for this registry is approximately 800 patients. Due to the low incidence and prevalence of the disease, the size of the registry has been chosen based on the expected availability of eligible patients to be enrolled in a three year time frame. The estimated recruitment rates were based on published articles and advice from one leading pediatric rheumatology site.

It is planned that a total of 800 patients will be enrolled to this registry in a ratio of 5:3 corresponding to the Humira arm or the MTX arm respectively. The sample size determination is based on the rate of serious infectious AEs in the Humira arm. Assuming a total of 500 patients with full 5 years of follow up in the Humira arm, a maximum total exposure to the Humira in this registry can be 2500 patient years. Typically a higher rate of dropout is expected in a registry compared to traditional controlled studies. Allowing for approximately 68% dropout, a total of approximately 1500 patient years exposure in the Humira arm will have approximately 97% power, using a two-sided test at level of significance  $\alpha = 0.05$ , to detect a rate of serious infectious AE of 4.8 events per 100 patient years from the rate of 2.8 events per 100 patient years previously seen in this population in Study DE038.

Due to low frequencies of malignancies and congestive heart failure (CHF), patients will be followed for an additional 5 years.

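### An MTX-arm child in direct-to-HCP follow-up who starts Humira without re-consenting stays in the MTX reference for the observational rates, and no exposure-based summary picks up the later events

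*Supplement*

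**What the plan says.** **Arm in HCP follow-up (6.2).** "Patients participating in the HCP follow-up process may not switch registry treatment arms during the HCP follow-up process". To move to Humira, an MTX patient must re-consent at a registry site. "All data collected post authorization will be included in analysis of the treatment arm indicated at the time of patient authorization". The sentence then adds one exception, which ends this assignment: "or until the date the patient re-consents in the registry".

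**When re-consent is possible (6.1, 6.5, 10.6).** Re-consent into the Humira arm is open only until that arm has finished enrolling. Section 10.6 bases the registry's size on the "expected availability of eligible patients to be enrolled in a three year time frame"; follow-up lasts up to 10 years.

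**Observational rates (10.3.1, 10.2).** "The AEs summaries will also include SAEs and AEs of Special Interest collected through the HCP process". The window runs from the first registry day to last contact, whatever the treatment. The observation period in 10.2 includes HCP time and is not cut at a first Humira dose.

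**Other safety summaries (10.2 to 10.3.4).** MTX exposure duration is cut at the first Humira dose, but it serves only the treatment-emergent rates. Those rates and the treatment-interruption summaries leave out HCP data.

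**MTX patients still in the full registry (6.1, 6.6.4).** After the Humira arm closes, those who move to Humira are discontinued from, or excluded from, the MTX arm but may be followed on. Section 6.6.4 adds that "if a patient in MTX treatment arm begins Humira therapy, Humira will be considered a concomitant medication".

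**Drug dates in HCP follow-up (7.3, 6.7.2).** Section 7.3 says "the start and stop dates for Humira and/or MTX will be collected on an annual basis". For ages 4 to 17, Section 6.7.2 lists medication use on the HCP questionnaire only through Year 5.

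**The concern.** Section 5.0 makes long-term Humira safety the primary objective, with MTX-treated patients as the reference group. Section 10.6 gives the rarity of malignancy and CHF as the reason for the second five years. In those years the HCP process collects malignancies, CHF, hospitalizations, surgeries and deaths for ages 4 to 17.

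The 6.2 rule lets consent status, and not the drug taken, decide where these events go. A child who left the full registry as an MTX patient and was later given Humira adds Humira-exposed time, and any late event, to the reference. The same experience is missing from the Humira side. In a safety registry that is the unfavourable direction of error: if Humira raises the risk, the reference rate rises and the contrast shrinks.

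**Working it through.** **1. The plan's own figure, and whether this point touches it.** Section 10.6 claims about 97% power for 4.8 against 2.8 serious infections per 100 patient-years with 1500 patient-years on Humira.
- Expected events: 1500 × 2.8/100 = 42 and 1500 × 4.8/100 = 72.
- An exact Poisson upper-tail test at 0.025 rejects at 56 or more events (tail 0.0223) and has 97.8% power. The figure reproduces.
- It uses Humira-arm exposure and a fixed historical rate only. MTX-arm data do not enter, so the power is unaffected.

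**2. Where a late event is counted.** Take an MTX child in HCP follow-up who starts Humira and later has a malignancy.

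| Summary | Re-consented while the Humira arm was open | Did not, or could not, re-consent |
|---|---|---|
| Observational (10.3.1) | Humira arm from re-consent | MTX arm, events and person-time |
| Treatment-emergent (10.3.2, 10.3.3) | By the usual Humira-arm rules | Excluded as HCP data |
| Interruption (10.3.4) | By the usual Humira-arm rules | Excluded as HCP data |

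In the right-hand column the event appears once, under MTX. After closure every such child falls in that column.

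**3. How long the misplaced time can be.** Follow-up is 10 years in total. If enrolment takes the planned three years, the first child enrolled has 10 − 3 = 7 years left at closure. The last has almost 10, but must first leave the full registry and then start Humira. The misplaced time is therefore shorter than 10 years for any child.

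**4. Direction, and an illustration of size.** Let *f* be the share of all MTX-arm observation time that falls after a Humira start, and *R* the true Humira-to-MTX rate ratio. Assume that all Humira-arm time runs at the Humira rate and that this rate applies from the first dose.

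MTX-arm rate, relative to MTX-only = (1 − *f*) + *f R*; observed ratio = *R* / (1 − *f* + *f R*).

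| Assumed *R* | *f* = 0.1 | *f* = 0.3 | *f* = 0.5 |
|---|---|---|---|
| 1.5 | 1.43 | 1.30 | 1.20 |
| 2 | 1.82 | 1.54 | 1.33 |
| 3 | 2.50 | 1.88 | 1.50 |

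Example: 2 / (0.7 + 0.3 × 2) = 2 / 1.3 = 1.54. Both *f* and *R* are assumptions; the protocol gives neither. HCP time is only part of MTX-arm time, so *f* from this source cannot exceed the HCP share.

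**The case against.** - **The observational summary is meant to ignore treatment, and no between-arm test is planned.** This is true: the output is rates with 95% confidence intervals. But MTX is the stated reference, so the two rates will be read side by side. Arms follow the physician's choice, so no randomisation needs protecting by analysing as assigned.
- **Exposure-based summaries exist.** They do, and MTX exposure is cut at the first Humira dose. They exclude HCP data, so they do not help here.
- **An as-treated table could sit in a separate SAP.** None is among the documents. However, 6.2 is a positive rule, and such a table would depart from it unless 6.2 allowed it.
- **Starters leave the MTX arm after closure.** Sections 6.1 and 6.6.4 say so for the registry in general. They do not say which arm the later observational data join, and 6.2 is specific to HCP follow-up. This is a conflict to reconcile; it does not cancel 6.2.

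Three stronger readings are tempting and are not supported. A reader might infer that the arm is frozen whatever the child later takes; the re-consent exception in the same sentence rules that out. A reader might infer from the concomitant-medication clause that full-registry starters are certainly counted under MTX; the text leaves this open. A reader might size the bias with the 4.8 and 2.8 of Section 10.6. Both are serious-infection rates for the Humira power calculation, and 2.8 comes from Study DE038, a prior Humira study, so it is not an MTX rate.

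**Conclusion.** The point holds for MTX-arm children in HCP follow-up who start Humira without re-consenting, and so for all who start after the Humira arm closes. Their later malignancies, CHF, deaths and person-time are placed in the MTX reference, and no other planned summary recovers them. If Humira raises the rate, the descriptive contrast moves towards no difference. The amount cannot be derived from the documents. The illustration shows the mechanism only and assumes an immediate effect of Humira, which is doubtful for malignancy. For full-registry patients who start Humira after closure, the finding is an unresolved assignment, not a demonstrated misplacement. The sample-size statement is not affected.

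**What to change.** 1. In 10.3.1, and in the observation-period definition in 10.2, add an observational table for malignancy, CHF and death split at the first Humira dose: MTX, never Humira, up to that dose; ever Humira from it. Move events and person-time together, using the dates in 7.3 and 6.6.11.
2. Report it beside the table by arm at authorization, and amend the 6.2 sentence to permit it.
3. State which arm holds the observational data of full-registry MTX patients who start Humira after closure, so that 6.1, 6.6.4 and 6.2 agree.
4. Reconcile 6.7.2 with 7.3 on HCP medication data, so that Humira and MTX dates exist for Years 6 to 10 in ages 4 to 17.

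The cost is wording in these sections and one derived exposure variable; if 7.3 stands, no new data are needed. Start dates from annual HCP forms may be approximate. The split also does not remove selection: under 6.1, those who switch are non-responders, intolerant of MTX or in need of combination treatment. This is one more reason to show both tables.

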## **6.3 Number of Patients to be Enrolled**

This is a multicenter, non-interventional, observational registry of patients' diagnosed at any time with moderately to severely active polyarticular or polyarticular-course JIA, (defined as arthritis affecting 5 joints at the time of diagnosis of polyarticular or polyarticular-course JIA), prescribed and treated in a routine clinical setting either with Humira or MTX. Approximately 800 patients will be enrolled in the United States, EU countries, and Australia. Approximately 500 patients will receive Humira (alone or in combination with MTX) and 300 patients will receive MTX without Humira.

#### **6.4 Physician Selection Criteria**

It is expected that approximately 120 physicians from the United States, European countries, and Australia will participate in this registry. Approximately 40 to 45 physicians will be included based on participation in prior AbbVie Humira sponsored clinical JIA studies.

#### **6.5 Registry Duration**

The planned follow-up observation period is 10 years from enrollment into one of the treatment arms. The follow-up period for patients that switch from the MTX arm to the Humira arm will begin when they enroll into the Humira arm, in which case participation would be longer (i.e., up to 10 years from the time of the switch).

A patient may withdraw from the registry at any time without prejudice. If the physician decides it is in the best interest of the patient to discontinue Humira or MTX for any reason, treatment should be stopped. Physicians are encouraged to keep patients in the registry for a full 10-year observation period irrespective of future treatment decisions so important and complete safety and effectiveness information can be obtained. If the patient is not seen at a visit, efforts, i.e., phone, fax, letter, will be made to gather safety data through Year 10.

Patients in the MTX arm who are prescribed Humira treatment must be re-consented before enrolling in the Humira arm during the time that the enrollment period is open (i.e., until enrollment in the Humira treatment arm is complete).

If a patient withdraws or is withdrawn from the registry, this should be noted, along with the reason for withdrawal on the electronic study completion page. At the time of withdrawal from the registry, an assessment of the patient's current medical condition will be completed.

Patients who discontinue from the registry or transition to another HCP will be offered to participate in the direct to HCP follow-up process by their registry physician, as allowed

by applicable local regulations. If the patient (or Parent/Guardian for pediatric patients) agrees, a consent/assent and/or patient authorization for use/disclosure for data (as applicable) will be obtained.

Effectiveness measures will not be collected from patients participating in the direct to HCP process.

## **6.6 Registry Conduct**

Physicians will be provided with a registry kit that includes a protocol, parental informed consent and patient assent forms, and information material to enable access to electronic Case Report Forms (eCRF), including Serious Adverse Event (SAE) Report Forms, and specially designed eCRFs to collect assessment data and AEs of Special Interest (AESI). When applicable, information about the effectiveness of Humira therapy will be provided by the patients and their physician. Effectiveness of therapy provided by the patient will be collected with paper patient questionnaires and visual analogue scales called patient reported outcomes (PROs) for selfadministered assessments, if part of routine clinical care. Physicians will determine the appropriate therapy for each patient in accordance with the locally approved label. The decision to prescribe Humira (monotherapy or combination therapy with MTX) or MTX (without Humira) to the patients should be made separately from the decision to enroll them into the registry.

The physician will follow the patient during regular office visits at intervals as determined by routine clinical practice or as recommended by national guidelines.

At the enrollment (baseline) visit, the Investigator will complete the Enrollment eCRFs by obtaining and recording all of the available required information. AEs of Special Interest (Section 7.1.3) in addition to hospitalizations and surgeries meeting SAE criteria (Section 7.1.4) that occurred prior to the enrollment (baseline) visit will be collected on a specially designed questionnaire for entry into EDC.

At subsequent visits corresponding to the intervals in the registry activities (Table 1), the Investigator will complete the appropriate eCRF by obtaining and recording all available

[figure not shown]
information. Since this is an observational registry conforming to usual clinical practice, data will be collected from patient visits that most closely correspond to the protocol intervals in [Table 1](#). Months 1 and 3 (not required for patients who participated previously in an AbbVie sponsored Humira study), and Month 6 followed by routine office visits every 6 months through Year 5. For example, if a patient visits the investigator at Month 5, this is close to the protocol-defined 6-month visit, so data can be collected for this visit. If the same patient unexpectedly returns for a visit the investigator's site at a date closer to the 6 month visit, no further effectiveness data needs to be collected since the data was previously collected. Safety data that meets the criteria for collection should be collected regardless of protocol-defined registry visits.

For collection of Safety data, see [Figure 1](#) and [Figure 2](#).

**Figure 1. Registry Schematic for Polyarticular JIA Patients 4 to 17 Years of Age**

**With HUMIRA® , eow or Methotrexate (as directed)**

eow = every other week

[figure not shown]
\* For patients not rolling over from Study DE038 or Study M10-444.

\*\* Participation in the registry may be longer if patient switches from MTX arm to Humira arm.

\*\*\* The Direct to HCP Follow-up Process will collect events annually.

**Figure 2. Registry Schematic for Polyarticular JIA Patients 2 to < 4 Years of Age in Countries with Available Local Approval for this Group of Patients at the Time of Consent to the Registry**

